##### During the first 6 weeks

On a weekly basis, the following investigations must be performed:

- Physical examination, including vital signs and weight
- PS on ECOG scale
- Adverse events reporting
- Concomitant medications
- CBC including RBC, Hb, WBC and differential, platelets
- Biochemistry tests

On an every three-weeks basis, the following investigations must be performed:

- CA-125 concentration
- Electrocardiogram

For translational research:

- CCI [REDACTED]

Imaging at Day 43

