### Tumor evaluation

Tumor response will be evaluated according to RECIST 1.1. Tumor assessment will be performed within 21 days prior to treatment start, at Day 43 and then every 9 weeks until disease progression justifying further treatment and will require CT-scans of the pelvis and abdomen and (X-ray or preferably CT-scan) of the chest. MRI can be used for patients who are allergic to radiographic contrast media. Throughout the study, the same assessment technique must be used.

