## 7.6 Definitions and Derived variables

### 7.6.1 Definitions

Screened patient: A patient having consented

Re-screened patient: A patient who did not meet eligibility criteria when initially consented. This patient may fulfill criteria later and will be re-consented for screening.

Screened failed patient: A screened patient never treated in the study for any reason.

Treated patient: A patient having received at least one TG4050 dose.

Completed patient: Patient will be considered as completer if she received the treatment until:

- Disease progression or until the maximum number of administrations has been reached (20 injections of TG4050)
- occurrence of an AE due to DLT or linked to progressive disease
- Death

Baseline: Unless otherwise specified, baseline is the last measurement taken prior to the first injection of TG4050.

Baseline assessment for efficacy evaluations: In the context of baseline definition, the efficacy evaluations include in particular tumor evaluations and CA125 measurement. If baseline assessment is missing, results obtained at Day 1 can be used if assessments were performed prior to first TG4050 injection.

Baseline assessment for safety evaluations: the last available assessment before first TG4050 injection. If patients have no assessment as defined above, the baseline result will be missing. Baseline can be D1 if assessment was done before first TG4050 injection.

Study day:

- From first treatment administration, study day will be calculated using the start date of treatment as the origin, i.e. the study day will be calculated as (date of assessment) – (start date of study treatment) +1. Then study day 1 will be the first day of first study treatment administration.
- For pre-study treatment administration measurements, the study day will be negative and calculated as (date of assessment) – (start date of study treatment).

Cut-off date: For a given analysis (safety, final and follow-up analysis), data in the database with a date prior or equal to the cut-off date must be as clean as possible for the analyses. The cut-off date will be the date of the export.

Time window (to check visits out of this window):

- For the visits:
  - +/- 1 day for the first 6 weeks
  - +/- 7 days beyond the first 6 weeks
- For the tumor assessment:

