### 7.6.2 Derived variable

The following conventions will be used:

- 1 month corresponds to  $365.25/12=30.4375$  days.
- 1 year corresponds to 365.25 days.
- Temperature (°C):
  - from F to °C:  $\text{Temperature (°C)} = (\text{Temperature (F)} - 32) / 1.8$
- Weight (kg):
  - from Lbs to kg:  $\text{weight (kg)} = \text{weight (lbs)} \times 0.45$
- Height (cm):
  - from Inch to cm:  $\text{height (cm)} = \text{height(inch)} \times 2.54$

The following variables will be calculated:

- **Age in years:** the age at informed consent form (ICF) signature presented in whole years  
(year of ICF signature – year of birth)
- **Body Mass Index (BMI) expressed in kg/m^2:**  $\text{Weight (kg)} / \text{Height}^2 (\text{m}^2)$
- **Duration of an event (in days):** End date – Start date + 1
- **Time since initial diagnosis (Months):** (date of ICF signature – date of initial diagnosis)/30.4375

**Time to measurable relapse per RECIST 1.1 (months)** is defined as the time from the date of the first injection until relapse or documented progressive disease whichever occurs first. Time to measurable relapse will be censored if no progression is observed at the cut-off date for analysis. The censoring date will be the date of the last evaluable tumor assessment before the cut-off date.

Time to measurable relapse expressed in months =

((Date of documented relapse/disease progression) - date of first treatment injection) +1)/30.4375

or

(Date of last evaluable tumor assessment – date of first treatment injection +1)/30.4375 in case of censoring.

**Relative Dose intensity (RDI) (%)**: expressed as percentage and defined as the ratio of “delivered” to the “planned” dose intensity. As the dose is always the same ( $10^8$  / pfu), RDI is calculated as the ratio of number of injections received divided by the number of injections planned. A Relative Dose Intensity of 100% indicates that TG4050 was administered as planned, without delay and without cancellations.

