**Delivered Dose intensity ( $10^8$  pfu/week):**

If last dose before D43 visit (visit day  $\leq$  44)

- number of injections / [(Last dose date-1st dose date +7)/7]

If last dose on or after D43 visit (visit day  $>$  44):

- number of injections / [(Last dose date-1st dose date +7\*3)/7]

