**Planned Dose intensity ( $10^8$  pfu/week):**

If last dose before D43 visit (visit day  $<$  42): 1

If last dose on or after D43 visit (visit day  $\geq$  42):

Given xx the theoretical study day of visit Dxx

$$\frac{6 + \text{Int}\left[\frac{(xx - 1 + 21 - 7 \times 6)}{21}\right]}{(\text{Last dose date} - \text{1st dose date} + 21)/7}$$

For example, at visit D85; then number of injections should be:  $6 + \text{int}((85-1+21-42)/21) = 9$

**Duration of exposure (weeks):** (Last dose date-1st dose date + 1)/7

All laboratory parameters will be expressed in the International System (SI) of units and the intensity grade using CTCAE version 5. A grade of 0 will be assigned when the value is within normal limits. In the case a local laboratory normal range overlaps into the higher (i.e., non-zero) CTC grade, the laboratory value will still be taken as within normal limits and assigned a CTC grade of 0. When normal limits are missing and needed for intensity grade determination, the grade will be set at missing. If normal limits are missing but not needed, grade intensity will be calculated as usual with CTCAE ranges.

Laboratory values recorded as “value  $<$  x” or “value  $>$  x” will be handled as the formula:

- $x = x * \sum_{i=1}^{n+2} (9 * 10^{-i})$  if value recorded as “value  $<$  x” with n denoted the number of significant digits
- $x = x * (1 + 10^{-n+2})$  if value recorded as “value  $>$  x” with n denoted the number of significant

digits

for the calculation of descriptive parameters and for the value derived in standard units. Other methods could be investigated for specific parameters. In individual listings, they will be presented as “< x” or “> x”.

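### SAP 7.6.2 prints different D43 limits for delivered and planned dose intensity; programmed as printed, a last dose on days 42-44 with all 7 injections gives an RDI of 128-129%, where the SAP's own labels and count rule give 100%

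*SAP*

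**What the plan says.** SAP 7.6.2 first defines RDI as delivered over planned dose intensity. Because the dose is constant, it then reduces this to a count: "RDI is calculated as the ratio of number of injections received divided by the number of injections planned". It interprets the result as follows: "A Relative Dose Intensity of 100% indicates that TG4050 was administered as planned, without delay and without cancellations".

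The two component formulas follow.

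- **Delivered intensity.** The early branch opens "If last dose before D43 visit (visit day" and prints a limit of 44 or less. It adds 7 days to the interval from first to last dose. The late branch, for visit day above 44, adds 21 days.
- **Planned intensity.** The early branch carries the same verbal label but prints a limit below 42, and sets the planned value to 1 per week. The late branch opens "If last dose on or after D43 visit (visit day" and prints 42 or more. It takes the planned number of injections from the nominal visit ("Given xx the theoretical study day of visit Dxx") and divides by the actual first-to-last interval plus 21 days.

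SAP 7.6.1 gives visit windows of +/- 1 day in the first 6 weeks and +/- "7 days beyond the first 6 weeks". Protocol Appendix II B marks D43 as +/- 1 day and schedules an injection there, the seventh.

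**The concern.** Two formulas that form one ratio should change branch at the same point. Here the labels agree and the numbers do not. The delivered formula's limit of 44 also contradicts its own label, because it places the D43 visit in the branch for doses before D43. For a last dose in the D43 window, delivered intensity is spread over a 7-day tail and planned intensity over a 21-day tail, so the ratio is inflated.

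The SAP therefore gives two answers for the same patient, depending on whether the programmer follows the numbers or the words. Under the numbers, a patient who missed an injection would be listed above 100%. Stopping at this visit is not far-fetched, since the first on-treatment scan falls there (Protocol 6.2.3: "Imaging at Day 43"; Protocol 8.2.1: "Tumor assessment will be performed within 21 days prior to treatment start, at Day 43 and then every 9 weeks").

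The second question is whether 100% can carry the meaning that the SAP gives it. Protocol 7.3 foresees delayed injections for related adverse events, so a reader may use RDI to look for them.

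**Working it through.** **Inputs.** Injections on D1, 8, 15, 22, 29, 36, 43, then every 21 days up to 20 (Protocol 3.1 and Appendix II B); formulas and limits from SAP 7.6.2; windows from SAP 7.6.1. Last dose date minus first dose date equals the day of the last dose minus 1.

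**The SAP's own figure.** Planned injections = 6 + int((xx - 1 + 21 - 42)/21).

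- D85: 6 + int(63/21) = 9, as in the SAP's example.
- D43: 6 + int(21/21) = 7.
- D316: 6 + int(294/21) = 20, the protocol maximum.

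The planned count is sound; the problem lies in the branch limits.

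**Last dose in the D43 window, 7 of 7 given, printed limits.** Delivered uses the 7-day tail (day 44 or less). Planned uses the 21-day tail (day 42 or more).

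| Day of last dose | Delivered | Planned | RDI, 7 of 7 | RDI, 6 of 7 |
|---|---|---|---|---|
| 42 | 7/(48/7) = 1.021 | 7/(62/7) = 0.790 | 62/48 = 129.2% | 110.7% |
| 43 | 7/(49/7) = 1.000 | 7/(63/7) = 0.778 | 63/49 = 128.6% | 110.2% |
| 44 | 7/(50/7) = 0.980 | 7/(64/7) = 0.766 | 64/50 = 128.0% | 109.7% |

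The last column is the one before it times 6/7.

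**Same patients by the verbal labels.** D43 belongs to the late branch of both formulas, so the intervals cancel: 7/7 = 100% and 6/7 = 85.7% on each of the three days. The count rule gives the same values.

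**Reading of visit day.** If it means the actual day, days 42 to 44 are affected. If it means the nominal day, 43 satisfies both conditions (44 or less, 42 or more), so every patient whose last dose is the D43 visit is affected.

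**Delay, later phase.** D85 dose, the ninth, given on day 92, inside its window: delivered 9/((91 + 21)/7) = 9/16 = 0.5625. Planned is also 9/16, because it divides by the same actual interval. RDI = 100% although the dose was 7 days late.

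**Delay, weekly phase.** Planned is fixed at 1. D36 dose, the sixth, on day 37: 6/(43/7) = 97.7%. On day 41: 6/(47/7) = 89.4%. Lateness that carries through to the last dose lowers RDI here.

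**The case against.** The best defence is that the inflated values follow from only one way of reading the SAP. The labels on both formulas and the count rule all give 100%, so the 44 may be a slip that a careful programmer would resolve. That is right, and it limits the claim to an inconsistency with one wrong printed limit. It does not remove the point, because numeric limits are what usually gets programmed.

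A second defence is that the practical effect is close to nil. SAP 8.6.1 provides RDI by listing only, next to the number of injections and the duration of exposure. Protocol 9.5.4.2 does not ask for RDI. Delays appear in Listing 16.2.5.3 and in the action-taken item of the adverse event listing. This also stands.

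On delay, a reader might infer that RDI never responds to lateness. The weekly-phase figures show otherwise. A reader might also infer that a dose two weeks late would still show 100%. The documents do not settle that. A D64 dose given on day 78 lies in the D85 window (78-92), and a D85 dose given on day 99 lies in the D106 window (99-113). If the dose took the later label, RDI would fall to 8/9 = 88.9% or 9/10 = 90%. SAP 7.6.1 gives the windows for checking visits and does not say how a late dose is labelled. The secure case is a late dose inside its own window. Such a dose is permitted, which weakens the complaint but does not make it undelayed.

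**Conclusion.** Minor, but wrong as written. The printed limits of 44 and 42 conflict with each other, and the 44 conflicts with its own label. Taken literally, they overstate RDI by 28 to 29 percentage points for a patient with 7 of 7 injections whose last dose is in the D43 window. They also put a patient with 6 of 7 at about 110% when the count is 85.7%. These figures assume that the printed limits, not the labels, are programmed.

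The *without delay* wording has support only in the weekly phase. For last doses from D43 on, with the limits aligned, RDI is a pure count ratio. It cannot show lateness while the dose keeps its visit label.

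A reader might infer that some listed RDI is in error or that the safety conclusions are affected. The documents support neither. SAP section 4 reports 6 treated patients, nothing shows that any of them had a last dose on days 42-44, and RDI enters no summary or decision.

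**What to change.** 1. Use one switch point for both formulas, defined only by the visit label of the last dose: before D43, or D43 and later. Correct the delivered-intensity limit to match. This gives 100% (7/7) and 85.7% (6/7) on days 42, 43 and 44. Moving both formulas to the 44 limit instead would contradict the labels and give 102.1, 100.0 and 98.0% for 7 of 7.
2. Do not add a day limit beside the label, because the two tests can disagree. Suppose the D29 dose, the fifth, is given on day 42 and is the last. The label test gives 5/(48/7) against 1, or 72.9%. A day test gives 5 of 6 + int(7/21) = 6 planned, or 83.3%.
3. Delete *without delay*, or limit it to the weekly phase, and refer the reader to Listing 16.2.5.3 for delays.

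Whether RDI should be count-based or time-based throughout is the sponsor's choice and is not needed for this correction.

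The cost is an edit to the branch conditions and one sentence, and a rerun of one listed variable for 6 patients. If the listing already exists, only patients whose last dose was at D43 need checking for the inflated value.

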### Action taken regarding the IMP

- None: administration continues as planned in the protocol
- Delayed: administration following the occurrence of the event is delayed
- Cancelled: administration following the occurrence of the event is cancelled
- Stopped: administration is definitively stopped
- Not applicable: administration is already stopped, or study treatment not started yet

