##### 9.5.4.2. **Study treatment**

Exposure to TG4050 will be provided by listing and summarizing the number of injections and the duration of treatment.

The SAF will be used for all summaries and listings of study treatment. Analyses will be displayed separately for each cohort of treated patients.

The number of patients with dose omission will be presented along with reasons for the dose omission.

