### **8.6.1 Study treatment**

Duration of TG4050 exposure, number of TG4050 injections and Relative Dose Intensity (RDI) will be provided by listing. The total number of injections will also be displayed.

The safety population will be used for all listings of study treatment.

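### On its natural reading, RDI ignores injections cancelled after the last dose given, so 100% does not mean no delay and no cancellations

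*SAP*

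**What the plan says.** SAP 7.6.2 describes RDI as delivered over planned dose intensity. Because the dose is fixed, it reduces this to counts: "RDI is calculated as the ratio of number of injections received divided by the number of injections planned". It then interprets the top value: "A Relative Dose Intensity of 100% indicates that TG4050 was administered as planned, without delay and without cancellations".

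Delivered intensity is the number of injections over the weeks from first to last dose, plus one dosing interval. The early form, for a last dose before the D43 visit, is "number of injections / [(Last dose date-1 st dose date +7)/7". The later form is "number of injections / [(Last dose date-1 st dose date +7\*3)/7".

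Planned intensity is 1 per week in the early branch. In the later branch it is a planned count over the same last-dose denominator. The count is evaluated at a day introduced only as "Given xx the theoretical study day of visit Dxx". The SAP does not say which visit that is.

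On reporting, SAP 8.6.1 says: "Duration of TG4050 exposure, number of TG4050 injections and Relative Dose Intensity (RDI) will be provided by listing". Protocol 9.5.4.2 promises something more: "The number of patients with dose omission will be presented along with reasons for the dose omission". Protocol 8.2.2.4 (action taken regarding the IMP) keeps a cancelled dose apart from a definitive stop: "Cancelled: administration following the occurrence of the event is cancelled".

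**The concern.** Both intensities are tied to the last dose given. Doses that were due and cancelled between that dose and permanent discontinuation enter neither the numerator nor the denominator. The SAP nevertheless tells the reader that 100% rules out cancellations.

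Tolerability is part of the primary objective. A patient whose doses are cancelled and who then stops is one that a dose-intensity measure ought to pick out. As written, that patient gets a perfect score, while one who missed a single dose and resumed gets a lower one. The aggregate display that would compensate, the protocol's count of patients with dose omission by reason, appears neither in SAP 8.6.1 nor in the SAP's list of tables.

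**Working it through.** **Inputs.** The schedule is weekly for six weeks and then every three weeks, to a maximum of 20 injections (protocol 3.1). The flow chart in protocol Appendix II-B gives dosing days D1, 8, 15, 22, 29, 36, 43 and every 21 days after that. The formulas are those of SAP 7.6.2. The dosing histories below are constructed illustrations, not trial data.

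**Reproducing the SAP's figure.** The planned count at visit xx is N(xx) = 6 + Int[(xx − 1 + 21 − 42)/21]. At D85, N = 6 + Int(63/21) = 9, which matches the SAP's example. The formula also matches the schedule at every visit from D43 (7) to D316 (20), so the count itself is correct. The question is where it stops.

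**Cancellations after the last dose, then a permanent stop**

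- Last dose D22, with D29 and D36 cancelled. Delivered = 4 / [(21 + 7)/7] = 4/4 = 1. Planned = 1. RDI = 100%. Doses due: 6. Received over due = 4/6 = 66.7%. This branch does not use xx.
- Last dose D85, with D106 and D127 cancelled. Delivered = 9 / [(84 + 21)/7] = 9/15. Planned, with xx = 85, = 9/15. RDI = 100%. Doses due = N(127) = 11. Received over due = 9/11 = 81.8%.

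**Cancellations followed by another dose**

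- D64 cancelled, D85 given and last. Delivered = 8/15, planned = 9/15, RDI = 8/9 = 88.9%.
- D22 cancelled, D29 and D36 given, D36 last. Delivered = 5 / [(35 + 7)/7] = 5/6, planned = 1, RDI = 83.3%.

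**Delay**

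- D64 dose given 14 days late (day 78) and last. Delivered = 8 / [(77 + 21)/7] = 8/14. Planned, with xx = 64, = 8/14. RDI = 8/8 = 100%. The actual dates cancel out, so the delay does not show.
- D22 dose given on day 29 and last. Delivered = 4 / [(28 + 7)/7] = 4/5, planned = 1, RDI = 80%. In the early branch a delay does show.

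The examples avoid a last dose at about D43 because the branch limits there disagree (44 for delivered, 42 for planned). With all seven doses given and the last on day 43, the intensity formulas give [7/7] / [7/9] = 128.6%. That is a separate defect.

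**The case against.** **Stopping at the last dose is a coherent convention.** Delivered intensity, planned intensity and exposure duration all use the last dose date. This stands as a defence of the formula, but not of the sentence about 100%, which claims more than the convention can deliver.

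**The reading is not stated.** The SAP never says that xx is the visit of the last dose. That is fair for the later branch, although a denominator running to the last dose points that way. The early branch shows the same gap without using xx.

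**A reader might infer that cancelled doses never count.** They do when a later dose follows, as 88.9% and 83.3% show.

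**A reader might infer that these patients disappear from the report.** They do not. Listing 16.2.5.3 covers delayed, cancelled and stopped doses, Listing 16.2.5.2 shows administration per patient, and the AE listing carries the action taken. Only the aggregate omission count is missing.

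**A reader might infer that the safety conclusions are affected.** The documents do not support that. The primary endpoint is adverse events, RDI appears only in a listing, no decision rule uses it, and SAP section 4 reports six treated patients.

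**The scenario is narrow.** Under the protocol a dose-limiting toxicity leads straight to a permanent stop, and a lesser related event usually leads to a delay. Doses formally cancelled before a stop are possible, because protocol 7.3 leaves restart or discontinuation to a later decision, but this is not the usual path.

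**Counting every visit up to the stop date would create a new error.** With imaging on D43 and every nine weeks after, D106 is both a scan day and a dosing day. A patient stopped for progression at D106 and not dosed that day would score 9/10 = 90% without having had a dose cancelled before the stop. This stands, and it shapes the fix.

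**Conclusion.** The point holds for injections due and cancelled after the last dose given and before permanent discontinuation. For such patients RDI reads 100% where the share of due doses received is 66.7% or 81.8% in the two examples, and the SAP's stated meaning of 100% is false. The words on delay also fail after D43.

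After D43 the conclusion assumes that xx is the last-dose visit; before D43 it needs no such assumption. The documents do not show whether any of the six treated patients had this history. The practical effect is modest. Still, with six patients each listed value will be read individually, and one listing could show a cancelled dose beside an RDI that is defined to exclude it.

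**What to change.** In SAP 7.6.2:

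- Define xx explicitly.
- Add to the planned count any injection that was due and recorded as cancelled or omitted after the last dose and before the decision to stop permanently, up to 20 in total. Do not count a dose withheld at the visit where the stop is decided. State how a dose held as delayed and never given is classed.
- At minimum, limit the sentence on 100% to the absence of cancellations up to the last dose given, and remove the claim about delay.

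In SAP 8.6.1, restore the count of patients with dose omission, by reason, from protocol 9.5.4.2. Take it from the administration records for all reasons. The AE page alone would miss omissions not caused by an adverse event.

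The cost is SAP wording and a few lines of programming on data already planned for collection. RDI will be slightly lower for patients who stop after cancelled doses.
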